Statistical	reasons for non-completion will be summarized. Feasibility will be evaluated by analyzing
Considerations:	recruitment time, follow-up completion, and missing data. Primary and secondary outcomes
	will be assessed using paired t-tests, linear mixed-effects models, or repeated-measures
	ANOVA to account for individual variability. Gender will be analyzed as part of all statistical
	evaluations. All quantitative analyses will be performed using Stata or R.
	To ensure privacy, each participant will be assigned a unique code. A list linking these codes
	to participants' names will be stored on a password-protected server (Switchdrive), accessible
	only by the research team. All data from questionnaires, medical visits, smartwatch monitoring,
Data privacy	or blood tests will be stored anonymously, with no participant names, but linked to the unique
	code. Blood and urine samples will be labeled with the unique anonymous code assigned to
	each participant. This system guarantees confidentiality and protects the privacy of participants
	while handling both data and any applicable biological material.
	The scientific value of this study lies in its exploration of the impact of cultural prescribing on
	the well-being of older adults, particularly those managing lifestyle-related conditions. This
	approach is innovative in integrating arts and cultural activities into healthcare, an area with
	limited research in elderly populations. By assessing how older adults engage with cultural
	prescriptions, the study could provide valuable insights into improving healthcare interventions
	for this group, potentially informing future practices.
	The methodology is carefully designed to assess the feasibility and acceptability of cultural
	prescribing through a controlled study, with a control group receiving a cultural activity
	alternative (museum, concert, or show) to allow for comparison. By assigning participants to
	two groups and monitoring health outcomes using statistical methods, the study ensures a
	rigorous and scientifically sound approach that will provide preliminary insights into the
Ethical	effectiveness of cultural prescribing.
consideration	Regarding risks and benefits, the study presents minimal risks, primarily associated with the
	blood draw, medical examination, and monitoring through the smartwatch, which are common
	procedures in clinical research. These risks will be mitigated through appropriate medical

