#### Secondary objectives:

- 2. Test whether there is any indication of an improvement in health orientation.
- 3. Compare health orientation and health outcomes of those participating in the programme versus the control group.

The study hypothesizes that cultural prescribing (artistic and cultural activities as part of healthcare) will be feasible and acceptable to older adults, and that participation in the program will lead to improvements in health orientation and health outcomes compared to a control group.

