#### 3.3 Study design

The study will follow a mixed-method approach. It will be designed as a **double-arm feasibility study with a control group, incorporating baseline and post-intervention assessments.** A total of 100 participants will be recruited and screened by general practitioners (GPs) collaborating with the Institute of Family Medicine at USI to ensure they meet the inclusion criteria. Of these, 80 participants will be assigned to the experimental group and invited to enrol in an artistic or cultural course, selected from a curated selection based on recommendations from a link worker. The remaining 20 participants, matched to the experimental group in terms of gender, age, and medical condition, will serve as the control group and will not participate in these activities, but will be offered a free ticket for a museum, concert o show. Including a small control group in this feasibility study would allow testing of the randomisation procedure and understanding of how the control group would work. All participants will be monitored over time to evaluate the feasibility of the intervention and to assess its potential short-term and long-term effects, particularly in relation to health orientation and other secondary outcomes.

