#### 5 STATISTICS AND METHODOLOGY

#### 5.1. Statistical analysis plan and sample size calculation

#### **Quantitative analysis**

Participant characteristics will be summarized at baseline to provide an overview of the sample. For all analyses, statistical significance will be set at p<0.05, but results will be interpreted based on the strength of the evidence, with continuous p-values and 95% confidence intervals (CIs) reported. Acceptability of the programme will be assessed through participant take-up and retention. The range and average number of sessions attended will be reported, along with a summary of reasons for not completing the intervention. Feasibility of recruitment and research procedures will be evaluated by assessing the time required to recruit 100 participants and analyzing the proportion of participants completing follow-up measures along with the amount of missing data at baseline and follow-up. Primary and secondary outcome measures will be summarized at baseline and follow-ups to assess changes over time. To evaluate the impact of the intervention, statistical methods such as paired t-tests will be used to compare pre- and post-intervention scores on health outcomes. Additional statistical approaches, including linear mixed-effects models or repeated-measures ANOVA, may be applied to account for individual variability over time. Gender will be analyzed as part of all statistical evaluations. All quantitative analyses will be performed using Stata or R. The

sample size of 100 participants is in line with similar feasibility studies in the field. Given that feasibility studies typically aim to assess the viability and practicality of an intervention rather than definitive outcomes, a sample size of 100 is appropriate for evaluating the key aspects of program implementation and data collection methods while providing insights for future larger-scale trials.

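### Section 5.1 evaluates the intervention's impact with paired before-after t-tests and states no between-arm contrast, so secondary objective 3 and the hypothesis have no matching analysis

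*Protocol*

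**What the plan says.** Section 5.1 (Quantitative analysis) introduces its method as the way to evaluate the intervention's impact: "statistical methods such as paired t-tests will be used to compare pre- and post-intervention scores on health outcomes". It then says that "linear mixed-effects models or repeated-measures ANOVA, may be applied to account for individual variability over time". The threshold is general: "For all analyses, statistical significance will be set at p<0.05".

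The synopsis (Statistical Considerations) states that primary and secondary outcomes "will be assessed using paired t-tests, linear mixed-effects models, or repeated-measures" ANOVA. The three methods are alternatives, and no arm term is mentioned.

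The aims are comparative. Secondary objective 3 in section 3.1 is to "Compare health orientation and health outcomes of those participating in the programme versus the control group". The hypothesis in the same section is that "participation in the program will lead to improvements in health orientation and health outcomes compared to a control group". Section 3.3 supplies the groups: "80 participants will be assigned to the experimental group", and 20 controls are matched on gender, age and medical condition.

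**The concern.** A paired t-test asks whether people changed between two visits. Objective 3 asks whether the two arms differ. The first does not answer the second, and the only firm commitment in section 5.1 is to the first. The mixed model or ANOVA is permitted rather than required, and its stated role is to handle variation within people over time.

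If the section is followed as written, two things are at stake. The 20 controls would contribute nothing to the evaluation of impact. And any movement common to both arms would be read as a programme effect at p<0.05. The study is meant to prepare a future RCT, so a before-after result labelled as impact could mislead that decision.

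There is a smaller problem in the synopsis. Its sentence applies paired tests to the primary outcomes too, but sessions attended, recruitment time, follow-up completion and missing data have no pre-intervention value to pair with.

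**Working it through.** **No plan figure to reproduce.** The protocol gives no power, effect size or SD; its 100 participants rest on precedent. Only 80 + 20 = 100 can be checked, and it agrees.

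**Inputs from the protocol.** 80 experimental and 20 control participants (section 3.3); significance at 0.05 (section 5.1; two-sided is assumed because sidedness is not stated).

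**Assumptions not in the protocol.** No true intervention effect; the same drift d in both arms, in units of the SD of the change score; equal SDs; comparable arms; dropout of 0% or 20%.

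**Step 1: paired t-test in the experimental arm.** The statistic is noncentral t with n − 1 degrees of freedom and noncentrality d√n.
- For n = 80, √80 = 8.94, so d = 0.2 gives 1.79 and d = 0.3 gives 2.68.
- The table shows the exact two-sided probability of p<0.05.

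| Shared drift d (SD of change) | 80 people | 64 people (20% dropout) | All 100 pooled |
|---|---|---|---|
| 0 | 5% | 5% | 5% |
| 0.1 | 14% | 12% | 17% |
| 0.2 | 42% | 35% | 51% |
| 0.3 | 76% | 66% | 84% |

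Simulation (20,000 runs, n = 80) gave 43% at d = 0.2 and 75% at d = 0.3. With no drift the paired test keeps its 5%.

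**Step 2: between-arm test of change, 80 against 20.** A shared drift cancels in the difference. Simulated rejection was 4.8% to 5.2% for drifts of 0 to 0.5 SD.

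**Step 3: separate paired tests in each arm.** These do not replace a contrast. With d = 0.3 and no effect, the paired test is significant in 76% of experimental arms but only 25% of control arms, because 80 is larger than 20. In 57% of such null studies the result reads as significant in the experimental arm and not in the control arm.

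**Step 4: precision of the arm difference.** √(1/80 + 1/20) = √0.0625 = 0.25.
- On change scores: half-width of the 95% CI about 1.985 × 0.25 = 0.50 SD of change (0.56 with 64 and 16 completers). Power is about 22% for a true difference of 0.3 SD, 51% for 0.5 SD and 79% for 0.7 SD.
- Adjusted for baseline, with baseline-to-follow-up correlation r: 1.985 × 0.25 × √(1 − r²), in SDs of the outcome. For r = 0.5 this is 0.43; for r = 0.7 it is 0.35. Both are before dropout, and r is assumed.

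**The case against.** **The control arm is not excluded.** The synopsis (Number of Participants) speaks of assessing preliminary differences between the groups, and section 4.3 promises adjustment for confounders in the statistical models, which a paired t-test cannot deliver. A mixed model could carry an arm-by-visit term, and its exact terms are often left to an analysis plan that is not shown. This stands in part: a reader might infer that the protocol rules out a comparison with controls, and it does not. But section 5.1 does more than stay silent on model terms. It commits to a within-person method for impact and gives the optional models a different job.

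**Paired changes have a use.** Objective 2 asks for any indication of improvement in health orientation, which can be read as a within-person question. This stands, so within-arm estimates should be kept.

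**The drift is assumed.** This also stands. A reader might infer that false improvement is expected here, from three arguments the documents do not carry:
- *Regression to the mean.* Some entry conditions are uncontrolled, but GPs select patients before a separate baseline visit (section 4.2). If the correlation is the same between any two occasions, the expected change from that baseline to follow-up is zero. Only two of the seven qualifying conditions are defined as uncontrolled, and no one is selected on health orientation or mood. No figure can be put on it.
- *Season.* Summer baselines and winter 6-month visits are likely under the planned dates, but the 12-month visit returns to about the same season, and the direction of any shift is unknown. It could hide improvement as easily as mimic it.
- *Shared courses.* The number of courses, the group sizes and the intraclass correlation are not given, and a random course effect with few clusters in one arm is debatable.

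**The synopsis sentence is a summary.** The sentences before it treat acceptability and feasibility descriptively, and section 5.1 confines paired tests to health outcomes. The wording is still wrong and easily corrected.

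**The study is about feasibility.** No conclusion on the primary objective depends on this test, and section 5.1 disclaims definitive outcomes. That limits the consequence but leaves objective 3 without an analysis.

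**Conclusion.** The point holds as a mismatch between aim and method. The stated evaluation of impact is a before-after test, while objective 3 and the hypothesis require a comparison with controls that is nowhere specified. The mismatch rests on the protocol's wording alone.

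The error rates are conditional: about 42% to 76% against about 5%, if both arms share a drift of 0.2 to 0.3 SD of change, if there is no true effect, and if the arms are comparable. The documents support neither a size nor a direction for the drift, so the plan could mislabel a shared change as an effect; it cannot be said that it will.

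The 5% is also a best case. Section 4.3 assigns participants by matching, although section 3.3 mentions testing a randomisation procedure. An arm comparison removes trends common to both arms but may remain confounded.

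**What to change.** In section 5.1 and the synopsis:

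1. Name the analysis for objective 3 as the baseline-adjusted difference between arms at 6 and 12 months with 95% CI. Estimate it from one linear mixed model with baseline value, arm, visit, arm-by-visit, gender, age and condition, and a random participant effect.
2. Report within-arm changes, for objective 2, as estimates with 95% CI, and state that they are not evidence of intervention impact.
3. In the synopsis, limit the paired tests and models to the secondary outcomes, and report the primary outcomes as proportions or means with 95% CI.
4. Label the arm difference as exploratory and possibly confounded because of assignment by matching.

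The cost is wording; no new data or participants are needed. The downside is that 20 controls give the wide interval shown above, and fewer results will reach p<0.05.

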#### **Qualitative analysis**

Interview transcripts will be checked for accuracy against the audio recordings by a designated researcher, deidentified (with the removal of specific names and locations to maintain participant confidentiality), and imported into NVivo V.12 for data management. An inductive thematic analysis will be conducted to identify potential mechanisms of action of the program, describe experiences, and explore barriers to engagement. Two researchers will independently review and familiarize themselves with an initial set of transcripts, identifying meaningful fragments of text and generating preliminary codes that align with the study's research aims. These initial codes will be entered into NVivo, where the remaining transcripts will be coded systematically. As the analysis progresses, new codes will be developed based on emerging data, while existing codes will be applied to relevant text fragments. Codes will then be organized into groups reflecting similar topics, with a focus on elucidating potential mechanisms of action of the program and barriers to engagement. These topic groups will serve as the foundation for the development of preliminary and final themes. Ongoing discussions among the research team will ensure rigor and coherence in theme development, with continuous peer review and validation to refine and finalize the thematic framework.

#### 5.2. Handling of missing data and drop-outs

After assessing the type and quantity of missing values, a sensitive analysis will be also performed using different approaches to eliminate possible biases due to these values.

In the event of drop-outs, participants who withdraw from the study before starting the artistic or cultural activity will be replaced by recruiting new participants to maintain an adequate sample size. This ensures that the study continues to have enough participants to evaluate the feasibility and outcomes effectively.

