#### 3 STUDY OBJECTIVES AND DESIGN

#### 3.1 Hypothesis and primary objective

Primary objective:

1. Explore programme feasibility and acceptability by assessing programme uptake, attendance

rates, reasons for non-attendance, and barriers to engagement.

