#### 3.2 Primary and secondary outcomes

#### **Primary outcome**

Uptake and feasibility of recruitment and research procedures

Uptake will be assessed both quantitatively and qualitatively. The quantitative assessment will include the range and average number of sessions attended by participants, as reported by cultural facilitators, while the qualitative assessment will explore reasons for non-attendance and barriers to engagement among participants. To enhance practicality, attendance will be measured based on sessions attended with the link worker, alongside standardized measures of the types of cultural activities recommended and attended, and self-reported participation in these activities. Feasibility of recruitment procedures will be evaluated by measuring the time required to recruit 100 participants, the number of individuals screened, and the number of eligible individuals who chose not to participate, as reported by GPs. Feasibility of research procedures will be assessed through the proportion of participants who complete follow-up assessments at each timepoint and the extent of missing data at both baseline and follow-ups. These measures will provide insights into the practicality of implementing the intervention and conducting research within this population. A measure of uptake will also be applied to the control group to evaluate if they did independently engage in cultural activities.

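### The rule in Protocol 5.2 that replaces people who withdraw before starting the activity can inflate uptake, the primary outcome, unless they stay in the denominators

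*Protocol*

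**What the plan says.** Protocol 5.2 fixes a conduct rule: "participants who withdraw from the study before starting the artistic or cultural activity will be replaced by recruiting new participants". Its stated purpose covers feasibility as well as health outcomes: "This ensures that the study continues to have enough participants to evaluate the feasibility and outcomes effectively".

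Feasibility is what this trial is for. The primary objective in 3.1 is to "Explore programme feasibility and acceptability by assessing programme uptake, attendance" and related measures. The primary outcome in 3.2 is "Uptake and feasibility of recruitment and research procedures". On how uptake is measured, 3.2 says "Uptake will be assessed both quantitatively and qualitatively", and then "The quantitative assessment will include the range and average number of sessions attended by participants". Section 5.1 adds: "Acceptability of the programme will be assessed through participant take-up and retention".

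On numbers, 3.3 plans 100 people: "Of these, 80 participants will be assigned to the experimental group", and the other 20 are controls matched on gender, age and condition.

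Section 4.3 gives the order of events: consent and baseline, assignment to a group, link-worker contact some 3-4 weeks after baseline, then the course. Controls are sent a ticket and have no course to begin.

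**The concern.** Someone who consents, completes baseline, is assigned to the experimental group and then leaves before the first session has not taken up the programme. In a feasibility study that is a result. Under 5.2 it becomes a reason to recruit somebody else.

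The interval in which the rule operates includes the time when people decide whether to take part in a course. Sections 3.3 and 7.1 say that participants are told about the study only in general terms at consent. According to 3.4, the link worker then describes the actual offer. A person who withdraws after that conversation may well be declining the programme itself.

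No listed measure clearly picks these people up. The GP-reported refusals in 3.2 come before consent. Attendance is averaged over participants, which after substitution may mean the topped-up group. Sections 4.2 and 3.3 look ahead to a larger randomised trial, whose planning would rest on these uptake and retention figures.

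The rule also acts unevenly between the groups. It can select the experimental group for willingness to start, while no matching filter applies to controls.

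**Working it through.** **1. The plan's own figure.** Experimental 80 + control 20 = 100, as stated in 3.3. Section 5.1 supports this total by reference to similar feasibility studies. There is no expected uptake, withdrawal rate or precision target, so nothing further can be reproduced.

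**2. Inputs for the illustration.** People retained in the experimental group after replacement: 80 (from 3.3). Number replaced: x = 5, 10 or 20 (my assumption, as the protocol gives no rate). Mean sessions among the 80: 15 of at most 25 (the maximum is from 3.4, the mean is assumed). Follow-up completion among the 80: 85% (assumed).

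**3. Share of assigned people who did not withdraw before starting.** With everyone assigned counted, the share is 80/(80 + x). With the replaced people dropped, it is 80/80 whatever x is.

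| Replaced x | Assigned | All assigned counted | Replaced people dropped |
|---|---|---|---|
| 5 | 85 | 80/85 = 94.1% | 80/80 = 100% |
| 10 | 90 | 80/90 = 88.9% | 80/80 = 100% |
| 20 | 100 | 80/100 = 80.0% | 80/80 = 100% |

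The exact 95% interval for 80/80 is 95.5-100%. For 80/100 it is 70.8-87.3%. The two do not overlap, so sampling error would not cover the discrepancy at x = 20.

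**4. Mean sessions per assigned person.** Replaced people attended no sessions, so the mean is 15 × 80/(80 + x): 14.1, 13.3 and 12.0 for x = 5, 10 and 20, against 15 if they are dropped.

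**5. Follow-up completion.** Section 4.4 stops all procedures at withdrawal, so a replaced person completes no follow-up. The proportion is 0.85 × 80/(80 + x): 80.0%, 75.6% and 68.0%, against 85% if they are dropped.

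**6. Is replacement needed for precision?** Suppose 80 are assigned, 20% withdraw before starting and nobody is replaced. The estimate is 64/80 = 80.0%, exact 95% interval 69.6-88.1%, or about 9 points either side. Uptake can be estimated usefully without topping up.

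**7. Who is outside the rule.** It applies to people who withdraw from the study. Someone who never attends a session but stays for assessments is not replaced and counts as zero sessions.

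**The case against.** The strongest reply is that recruiting a substitute does not exclude the original person from analysis. Section 5.2 never says that withdrawn people leave the uptake or retention summaries. Section 4.4 keeps their data up to withdrawal in coded form, 4.3 records dropout reasons with a view to adjustment, and 5.1 summarises reasons for non-completion. Denominators are often left to a statistical analysis plan. This stands in part: exclusion is implied, not stated, and the information needed for a correct denominator is kept. It does not dispose of the point. The protocol itself fixes the replacement rule and justifies the topped-up sample as the one for evaluating feasibility. Adjusting for dropout is also not the same as counting these people as non-uptake.

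A reader might go further than the text allows in four ways:

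- **That everyone who fails to take up the programme is removed, so uptake will be reported as 100%.** This would need every non-starter to withdraw formally and every withdrawn person to be dropped. Non-attenders can stay in the study, and 3.2 measures uptake in several ways, including link-worker sessions, not just as a proportion starting.
- **That every pre-start withdrawal is a refusal of the course.** Some may come before assignment, and 4.4 also allows withdrawal for a new or worsening illness.
- **That the rule can act only in the experimental group and destroys comparability.** Section 5.2 names no arm, and the comparison is an exploratory one of 80 against 20. The rule acts mainly in the experimental group, because controls have no course to start, and it weakens the comparison.
- **That the rule must be deleted.** Keeping everyone in the denominators removes the bias even if course places are refilled.

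**Conclusion.** The concern holds in a conditional form. Following 5.2 means that many failures of uptake in the experimental group lead to substitution, in a study whose primary outcome is uptake. If replaced people are left out of the denominators, uptake, attendance, retention and follow-up completion are all biased upward. The direction is certain under that condition; the size is not known. For 5, 10 or 20 replaced against 80 retained, the overstatement of the share not withdrawing before the start is 6, 11 or 20 percentage points. Those figures are a worst case on denominators and rest on assumed withdrawal counts. The effect on the comparison with controls is a secondary weakness. The rule also leaves the recruitment-time measure ambiguous, since replacements may or may not be included in the time to reach 100.

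**What to change.** Amend 5.2 to say the following:

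- Replacements may be recruited to fill course places.
- Every assigned participant, including anyone who withdraws before starting, stays in the denominators for uptake, attendance (as zero sessions), retention and follow-up completion, and is analysed in the assigned group.
- The number of pre-start withdrawals and the number of replacements are reported by arm with reasons. Any withdrawal before assignment is shown separately.
- The time to recruit the first 100 is reported apart from the time spent recruiting replacements.

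The cost is a few sentences in 5.2 and some extra lines in the participant flow table. The data are already to be collected under 4.3 and 4.4. Reported uptake will be slightly less favourable.
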